As part of the preparedness activities for safety surveillance of COVID-19 vaccines, this template protocol provides a template for quickly developing a full study protocol to perform vaccine safety evaluation studies to quantify potential risks through the secondary use of electronic healthcare databases. The ACCESS project has developed several template protocols, that address: vaccine coverage, vaccine effectiveness and vaccine safety.

To allow all countries to participate and to utilize maximum capacity in Europe, protocols are divided in those that use primary data collection (e.g. hospital based), and those that rely on the secondary use of available electronic health care data.

This template safety protocol is for the evaluation of safety of COVID-19 vaccine(s) using population based electronic health record databases in Europe. In order to use this specific protocol, electronic health care data on population, events and COVID-19 vaccine administration are required.

The potential designs for safety evaluation of vaccines studies include the cohort, case-control, self-controlled case series (SCCS), self-controlled risk interval (SCRI), and case-crossover (CCO). Electronic health care data source requirements for the application of each study design are described in **Table 1**.

Table 1. Linkable electronic health care data elements for Cohort, Case-Control, SCCS, SCRI, and CCO designs

Design	Data Elements			
	Listing of all population members	Events	Covariates	Vaccine
Cohort	✓	✓	✓	✓
Case-Control	✓	✓	✓	✓
SCCS	X	✓	✓	✓

¹ https://ec.europa.eu/health/sites/health/files/vaccination/docs/2020_strategies_deployment_en.pdf

SCRI	X	✓	✓	✓
Case-Crossover	X	✓	✓	✓

Checkmark indicates design requires data element or feature; X indicates data element or feature is not required

As part of the harmonization of COVID-19 vaccine safety monitoring during the clinical development phase, the Coalition for Epidemic Preparedness Innovations (CEPI) has created a preliminary list of AESI for COVID-19 vaccine safety monitoring together with the Brighton Collaboration (SPEAC, 2020).

Within the ACCESS project, a list of AESI has been created which was approved by EMA (*EUPAS37273*). The listed AESI may not become real safety concerns but we should be ready to address them as they might potentially derail vaccination programs if they occur.

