9.1.4 Case-crossover (CCO)

Retrospective (multi)-database case-only study that includes subjects who experienced << event >>, independent of vaccination. The CCO design considers the occurrence of << event >> as fixed event and the << COVID-19 vaccine >> exposure random. The design compares the odds of exposure in a specific time window retrospectively in time, where the odds of exposure is compared over these time periods. Index date for the case is the date of the event, index date for the control periods of the same person are distinct points in time prior to case occurrence. Index moment for the control window, should be distanced with at least the duration of the exposure window (**Figure 5**). It is likely that vaccinations will only be administered on weekdays therefore the index date for the control window should be matched on day of the week to have equal probability of exposure. Control periods should not extend in the period prior to launch of the vaccination since the probability of exposure would be zero. Due to unavoidable time trend in vaccination a case time control adaptation is required (Schneeweiss, 1997). The case-time-control design is an elaboration of the case-crossover design, which uses exposure history data from a traditional control group to estimate and adjust for the bias from temporal changes in prescribing.

Figure 5. Case-crossover design

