SCRI	From <<COVID-19 vaccine>> introduction	Subject who received at least 1-dose of COVID-19 vaccine and who experienced <<adverse event>>	Follow-up should begin on the day of vaccine exposure. Length of follow-up will be fixed and depend on the risk and control periods that may vary according to the event. Follow-up may be curtailed if censoring conditions are met.
CCO	From <<COVID-19 vaccine>> introduction	Subject who experienced << event>>	Start: after introduction of <<COVID vaccine>> in a country and other inclusion criteria and are met End: the index date of the event.

⁵Study population for pregnancy outcomes should be adapted and includes pregnant women only, specific inclusion criteria may be required.

Note to future investigators: this section provides guidance and should be adapted according to the type of study design implemented.

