9.6.2 Measures of Association

Measures of association and statistical methods for each of the signal evaluation study designs are presented in **Table 4** below.

Null hypothesis for the study will be:

- **Cohort:** H_0 : the incidence of << event >> in the index group is equal to the incidence of << event >> in the comparison group.

- **Case-Control:** H_0 : the odds of cases exposed to <<COVID-19 vaccine >> is equal to the odds of controls exposed to <<COVID-19 vaccine>>.
- **Self-controlled:** H_0 : the incidence of << event>> in the risk period is equal to the incidence of << event>> in the control period.

Table 4. Measures of association according to the type of study design

Study design	Events	Statistical method	Measures of association
Cohort	All events excluding pregnancy outcomes	Poisson regression or Cox regression (time-dependent covariates/exposure)	Rate ratio or Hazard ratio
	Pregnancy outcomes	Binomial or logistic regression	Prevalence or odds ratio
Case-Control/Case cross over	All	Conditional logistic regression	Odds ratio
Self-controlled	All	Conditional Poisson regression	Incidence Rate Ratio

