Case -control studies using health care data sources have the advantage of having recorded vaccination prior to case occurrence. Matching and restriction should be applied to deal with confounding. Main sources of bias could be selection bias (e.g. validation cannot be performed for all cases) and is related to exposure, or if validation is conducted in an unblinded manner.

The main strengths of self-controlled designs are the adjustment for time-invariant covariates and their suitability to assess acute events. For less acute events and long latency events, a long washout period will be required and any uncertainty about risk periods will lead to misclassification and attenuation of risk estimates. A major limitation of the CCO is that it should not be used if there are temporal trends in exposure.

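### The case-crossover section requires a case-time-control adaptation, but its case-only description and Tables 1 and 3 leave out the control group, and Section 9.8 and Annex 3 do not name the adaptation

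*Protocol*

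**What the plan says.** Section 9.1.4 of the Protocol opens the case-crossover (CCO) description with "Retrospective (multi)-database case-only study that includes subjects who experienced << event >>, independent of vaccination". Later in the same section it states "Due to unavoidable time trend in vaccination a case time control adaptation is required" and says that the adapted design "uses exposure history data from a traditional control group to estimate and adjust for the bias from temporal changes in prescribing". It also limits the control windows: "Control periods should not extend in the period prior to launch of the vaccination since the probability of exposure would be zero".

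The other places that deal with the design read as follows.

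- **Table 1 (Section 7).** The CCO row has an X under the population listing; the cohort and case-control rows have a tick. The legend is "Checkmark indicates design requires data element or feature; X indicates data element or feature is not required".
- **Table 2 (Section 7).** CCO is ticked for 20 of the 35 listed events and marked X for 15. No footnote mentions vaccination trends.
- **Table 3 (Section 9.2.2).** The CCO population is subjects with the event, with no control group; the case-control row does define controls. Follow-up is given as "Start: after introduction of <<COVID vaccine>> in a country", plus the other inclusion criteria.
- **Table 4 (Section 9.6.2).** One row, "Case-Control/Case cross over", gives conditional logistic regression and an odds ratio. Case-time-control is not named.
- **Section 9.8.** "A major limitation of the CCO is that it should not be used if there are temporal trends in exposure".
- **Annex 3.** With vaccination trends present, CCO is rated O, meaning possible under certain circumstances. This O carries no footnote, whereas several other O entries in the framework do.

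**The concern.** A case-time-control analysis cannot be run on cases alone. It needs people without the event, observed over the same windows, to estimate how far uptake itself moved between the control window and the case window. Section 9.1.4 says so, but the tables that an investigator uses to choose a design (Tables 1 and 2) and to define its population (Table 3) describe a study without such people.

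Control windows always precede the case window. If uptake is rising, vaccination is more likely in the later window even when the vaccine has no effect on the event, and the odds ratio exceeds 1. If uptake is falling, the odds ratio is below 1. In a safety study the first produces a false signal and the second can hide a real risk.

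The order of decisions matters too. Section 9.1 tells the investigator to keep one design and delete the others. A data source chosen on the strength of the Table 1 entry, without a population listing, could not supply the required controls later.

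**Working it through.** The Protocol gives no sample size, power, CCO window length or uptake curve, so there is no stated figure to reproduce. The check has two parts.

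**1. Consistency.** Take the Section 9.1.4 requirement as the reference and ask whether each other place can deliver it.

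| Place | Delivers a control group? |
|---|---|
| 9.1.4, opening sentence | No: case-only |
| Table 1 | No: population listing not required |
| Table 3 | No: subjects with the event only |
| Table 4 | Compatible, but not named |
| Section 9.8 | Rules out CCO under trends; adaptation not mentioned |
| Annex 3 | Conditional; condition not stated |

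**2. Size of the bias if the adaptation is left out.** Assumptions: one dose, one case window and one adjacent earlier control window of W days each, no vaccine effect, and weekly uptake changing by a factor (1+g). A person vaccinated once can be exposed in only one of the two windows, so the matched odds ratio is the ratio of the two kinds of discordant case:

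null OR = (1+g)^(W/7)

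The 42 days are borrowed from the Protocol's SCRI example (Section 9.1.3.2), and the 2 days correspond to the 48-hour anaphylaxis risk period in Section 9.1.1. The 14 days and all values of g are assumptions.

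| Weekly trend g | W = 42 | W = 14 | W = 2 |
|---|---|---|---|
| -10% | 0.9^6 = 0.53 | 0.9^2 = 0.81 | 0.9^(2/7) = 0.97 |
| 0 | 1.00 | 1.00 | 1.00 |
| +5% | 1.05^6 = 1.34 | 1.05^2 = 1.10 | 1.05^(2/7) = 1.01 |
| +10% | 1.1^6 = 1.77 | 1.1^2 = 1.21 | 1.1^(2/7) = 1.03 |
| +20% | 1.2^6 = 2.99 | 1.2^2 = 1.44 | 1.2^(2/7) = 1.05 |

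A different assumed curve, with the vaccination rate rising linearly from launch and 42-day windows, gives cumulative uptake proportional to t squared:

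- event on day 84: (7056 - 1764)/(1764 - 0) = 5292/1764 = 3.0
- event on day 120: (14400 - 6084)/(6084 - 1296) = 8316/4788 = 1.74
- event on day 180: (32400 - 19044)/(19044 - 9216) = 13356/9828 = 1.36

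Day 84 is the earliest day on which two 42-day windows fit after launch, so 3.0 is the worst case on that curve.

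**False-positive rate.** With an assumed 100 discordant cases, an exact two-sided 5% test rejects at 61 or more, or 39 or fewer, in one direction. Its true size without a trend is 3.5%. With 42-day windows, the probability that a discordant case is exposed in the case window is OR/(1+OR):

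- +5% per week: 1.34/2.34 = 0.573; rejects in about 26% of studies
- +10% per week: 1.77/2.77 = 0.639; about 76%
- -10% per week: 0.53/1.53 = 0.346; about 84%

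**With the adaptation.** The case-time-control estimate is the case odds ratio divided by the control odds ratio. In a null simulation (400,000 persons, 42-day windows, trends from -10% to +20% per week) the plain estimate ran from 0.53 to 2.93. The case-time-control estimate stayed between 0.98 and 1.01, given controls who share the cases' uptake trend.

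**The case against.** The strongest reply is that Section 9.1.4 already makes the remedy mandatory. A biased odds ratio arises only if someone follows the tables and ignores that sentence, and a note in Section 9.2.2 says that the section holding Table 3 should be adapted. This stands. It lowers the severity, but does not remove the contradiction: the same section also says case-only, and Table 1 is consulted before any adaptation takes place.

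A reader might infer four stronger things, which the documents do not support.

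- **That no controls would be available.** Section 7 makes data on population, events and vaccination a condition of using the Protocol, and Section 9.2.1 defines the source population for every design as all registered individuals. The X in Table 1 contradicts this, but does not make case-time-control unworkable in general.
- **That Table 4 prescribes an analysis without controls.** Conditional logistic regression with an odds ratio also fits a case-time-control model. Its exact terms can be left to the analysis plan. Table 4 only fails to name the adaptation.
- **That all case-crossover entries should become conditional.** The 15 cells marked X in Table 2 include diabetes, narcolepsy and the pregnancy and neonatal outcomes. Annex 3 excludes CCO for long latency, gradual onset and undefined risk periods, and controls for trend cure none of these.
- **That the bias is always large.** For windows of about two days it is a few per cent.

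It is also fair to say that Table 2 rates properties of the event, while trend is handled in Annex 3, and that Section 9.8 may be meant for the unadapted design. Both readings are reasonable. That is why a footnote and a rewording are enough there.

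**Conclusion.** The point holds as an internal contradiction: Section 9.1.4 requires a control group that its own case-only wording and Tables 1 and 3 leave out, while Section 9.8 and Annex 3 do not name the adaptation that would reconcile them. Followed literally, the tables lead to a plain case-crossover under a trend that the Protocol itself calls unavoidable.

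The consequence is conditional. With 42-day windows the null odds ratio would be 1.77 at +10% per week and 0.53 at -10%; with 2-day windows it would be about 1.03 at +10%. Trend rates, window lengths and the 100 discordant cases are assumptions, not figures from the Protocol. The documents do not support saying that the plan as a whole yields a spurious odds ratio during roll-out. It should be corrected before the template is used for a case-crossover study, but it is not a fatal flaw.

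A secondary point concerns the control-window rule. Section 9.1.4 bars windows before launch because exposure was then impossible. The same reason applies before a person's own priority group became eligible, and neither Section 9.1.4 nor Table 3 goes that far. Controls matched on priority group and index date would share the same eligibility calendar, so this is a refinement.

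**What to change.** - **Table 1:** tick the population listing for case-crossover, labelled as case-time-control.
- **Table 3:** add to the CCO row a control group without the event at the index date, matched on age, sex, database and calendar index date and, where known, vaccination priority group.
- **Section 9.1.4:** drop or qualify the case-only description.
- **Table 2 and Annex 3:** footnote the 20 ticked CCO cells and the O for trends present as usable only as case-time-control. Leave the X cells unchanged.
- **Section 9.8:** say that it is the unadapted case-crossover that should not be used when exposure has temporal trends.
- **Table 4:** name case-time-control in the shared row, leaving the model terms to the analysis plan.
- **Control windows (Section 9.1.4 and Table 3):** where the date is known, start no control window before the later of launch and the person's priority-group eligibility.

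Cost: mostly text and table edits, plus sampling of controls. Sources without a population listing cannot use this design. Precision falls somewhat, because the control trend is estimated: the variance of the log odds ratio gains the reciprocals of the two discordant control counts, a term that shrinks as more controls are sampled.

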9.2 Setting

9.2.1 Source Population

The source population for each of the study designs will comprise all individuals registered in the health care data source during the study period for that data instance.

9.2.2 Study Period, Population and Follow-up Period

The study population will comprise all persons in the source population that are eligible for the study according to specific inclusion and exclusion criteria (such as study period, design requirements and exclusion of prior events, see generic conditions in **Table 3**).

Eligible individuals should be identified in each of the database using a pre-specified selection process and/or by applying pre-specified algorithms. Attrition diagrams should be made. Follow-up time should start at the moment that the latest of the inclusion criteria is met, follow-up ends at the earliest of the occurrence of censoring conditions or the last data draw down/data availability.

Study period, study population and follow-up period for signal evaluation study designs are summarized in **Table 3**.

Note to future investigators: this section provides general information and should be adapted according to the type of safety study conducted.

Table 3. Study period, study population, and follow-up period by study design

Study design/Analysis Method	Study period	Study population [§]	Follow-up period
Cohort	Index cohort: from <<COVID-19 vaccine>> introduction until last data collected Comparison cohort: from <<COVID-19 vaccine>> introduction until last data collected	Index: all subjects who received at least 1-dose of COVID-19 vaccine Comparison: all subjects matched for covariates such as age, sex, comorbidities, identified from same data source(s) who did not receive COVID-19 vaccine or alternative vaccine.	Start: latest of fulfillment of inclusion criteria or start of study period End: earliest of end of study period or censoring conditions
Case-control	From <<COVID-19 vaccine>> introduction until date protocol is implemented or data is available	Cases: Subjects with a diagnosis of << event>> in the study period. Controls: Subjects matched on age, sex, database and/or region without << event>> diagnosis at the time of index	From start of follow-up until index date The length of risk period ('look back period') should be defined according to the event under evaluation

		date. Index date = index date of the corresponding cases	
SCCS	From <<COVID-19 vaccine>> introduction until latest data available	Subject who received at least 1-dose of COVID-19 vaccine and who experienced <<event>>	Start: latest of fulfillment of inclusion criteria or start of study period End: earliest of end of study period or censoring conditions
SCRI	From <<COVID-19 vaccine>> introduction	Subject who received at least 1-dose of COVID-19 vaccine and who experienced <<adverse event>>	Follow-up should begin on the day of vaccine exposure. Length of follow-up will be fixed and depend on the risk and control periods that may vary according to the event. Follow-up may be curtailed if censoring conditions are met.
CCO	From <<COVID-19 vaccine>> introduction	Subject who experienced << event>>	Start: after introduction of <<COVID vaccine>> in a country and other inclusion criteria and are met End: the index date of the event.

⁵Study population for pregnancy outcomes should be adapted and includes pregnant women only, specific inclusion criteria may be required.

Note to future investigators: this section provides guidance and should be adapted according to the type of study design implemented.

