9.1.1 Cohort

Retrospective (multi)-database cohort study where index <<COVID-19 vaccinated>> subjects and reference (subjects not vaccinated with << COVID-19 vaccine>>: reference cohort) are compared for occurrence of << event>>.

The comparison cohort will be matched using as example frequency matching or propensity score matching for important covariates such as age, sex and comorbidities (including COVID-19 infection prior to reference date) and markers of health care utilization (Austin, 2011). The comparison cohort could be the following:

- A concurrent comparison cohort including subjects not vaccinated with <<COVID-19 vaccine>> at the time of study start, identified at the same date (+/- 7 days – eg. anchored on a healthcare visit or pharmacy dispensing) of the exposure date (1st vaccine dose in case of multi-dose vaccine) of the matched vaccinated subjects. This calendar date time matching will allow to control for the variation in the SARS-CoV2 circulation and will minimize the risk of immortal time bias given that the time period before vaccination is immortal. To test for the presence and magnitude of immortal time, the time

difference between cohort entry and the date of start of vaccine distribution should be calculated for each cohort member and the frequency distribution of immortal time compared between the vaccinated and unvaccinated cohorts.

- If <<COVID-19 vaccine>> is distributed concurrently with the seasonal influenza vaccine, persons receiving both <<COVID-19 vaccine>> and the seasonal influenza vaccine could be compared with those receiving the influenza vaccine alone.
- A comparison cohort including subjects vaccinated with alternative <<COVID-19 vaccine>> in the same week as the matched index subjects. This time matching will allow to control for the variation in the SARS-CoV2 circulation.
- In the instance where the risk period of <<event>> is well known, the comparison cohort may be the same persons as the index cohort, with the comparison person time chosen after the ending of the risk window. Time trends in events cannot be controlled for in this manner.

[figure not shown]
The incidence rate ratio of the <<event>> is calculated comparing the incidence rate in index with that in the comparison cohort. The required follow-up time will depend on the event under evaluation, this follow-up time should take into account the vaccination schedule (**Figure 1**).

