9.1.3.1 Self-controlled Case Series (SCCS)

Retrospective (multi)-database case-only study that includes subjects who were vaccinated with << COVID-19 vaccine>> and experienced << event>>.

The incidence rate ratio between a period of time hypothesized to be at increased risk due to exposure (“risk window”) and control window (All other time within an individual's observation period, that does not fall within the risk period) is calculated (Figure 3).

Figure 3. Self-Controlled Case Series

[figure not shown]

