9.1.3.2 Self-Controlled Risk Interval (SCRI)

Retrospective (multi)-database case-only study including subjects who were vaccinated with <<COVID-19 vaccine>> and experienced << event>>.

The risk and control windows should be pre-specified. The incidence rate ratio between a period of time hypothesized to be at increased risk due to exposure (“risk window”) and control window (a pre-specified time window occurring after the risk window) is calculated. The SCRI is a subtype of the SCCS design, with a pre-specified duration of the control period (Figure 4).

Figure 4. Self-Controlled Risk Interval design

[figure not shown]

Note: Example with a risk period of 42 days and a control period of 42 days

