9.3 Data Sources

The data sources for the exposures, events, and covariates will be listed in this section, including coding systems, data lag, and starting date of data availability. The size of the database and COVID-19 vaccination strategy should be included in this section. Validation data on relevant data elements should also be described.

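### Follow-up ends at the last data draw-down with no use of the listed data lag: SCRI and same-person cohort rate ratios are biased upward in early draws, and SCCS in either direction

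*Protocol*

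**What the plan says.** The general rule in Protocol section 9.2.2 is that "follow-up ends at the earliest of the occurrence of censoring conditions or the last data draw down/data availability". Table 3 repeats it in the cohort row and in the SCCS row, where the study period runs from vaccine "introduction until latest data available". The SCRI row gives no end to the study period. It says "Length of follow-up will be fixed and depend on the risk and control periods that may vary according to the event", and allows curtailment only for censoring conditions.

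Three passages fix where control time lies:
- SCRI (9.1.3.2): the control window is "a pre-specified time window occurring after the risk window". The figure note reads "Note: Example with a risk period of 42 days and a control period of 42 days".
- Cohort, same-person option (9.1.1): the index persons serve as their own comparators, "with the comparison person time chosen after the ending of the risk window".
- SCCS (9.1.3.1): control time is all other observed time "that does not fall within the risk period". Table 3 starts the study period at vaccine introduction, so time before vaccination is included.

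Section 9.3 asks for the data sources to be described, "including coding systems, data lag, and starting date of data availability". No section uses that lag to set the end of follow-up or to decide who is eligible.

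**The concern.** An event shortly before the draw may not yet be in the database, although the person-day on which it fell is counted. Follow-up that runs up to the draw therefore includes days with a falsely low event rate.

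For a between-person comparison matched on calendar date this matters less, because both groups lose events over the same dates. In a within-person comparison the loss depends on which window is later. Where control time always follows risk time, control events are under-counted relative to risk events and the rate ratio rises with no vaccine effect.

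The template is meant for rapid use soon after roll-out (section 7), when the most recent person-time forms a large share of the total. A spurious signal could then come from the extraction date alone.

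**Working it through.** The template gives no lag, rate or sample size, so there is no figure of its own to reproduce. The check asks what rate ratio is expected when the true value is 1.

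**From the Protocol:** 42-day risk and 42-day control windows (figure note, 9.1.3.2); SCRI control after risk; SCCS control equal to all other time since introduction; follow-up to the draw (9.2.2).

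**Assumed, not in the Protocol:** the draw is at day D after introduction; vaccination is uniform over days 0 to V; recording delay is exponential with mean m = 14, 30, 60 or 90 days and unrelated to vaccination.

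**Formulas.** An event on day t is in the data by D with probability 1 − exp(−(D − t)/m). For each vaccination date, let Lr and Lc be the risk and control days up to the end of follow-up, and er and ec the expected recorded events. The rate ratio θ solves the conditional Poisson score equation, summed over vaccination dates:

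Σ er = Σ (er + ec) · θLr / (θLr + Lc)

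**One case by hand.** A person is vaccinated 84 days before the draw, and m = 30.
- Risk window, share recorded: 1 − (30/42)(e^(−42/30) − e^(−84/30)) = 1 − 0.714 × (0.247 − 0.061) = 0.867.
- Control window, share recorded: 1 − (30/42)(1 − e^(−42/30)) = 1 − 0.714 × 0.753 = 0.462.
- Ratio: 0.867/0.462 = 1.88, although both windows are complete in calendar time.

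**All vaccinees, follow-up to the draw, true ratio 1:**

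| Design | D | V | m=14 | m=30 | m=60 | m=90 |
|---|---|---|---|---|---|---|
| SCRI | 120 | 120 | 1.31 | 1.59 | 1.85 | 1.99 |
| SCRI | 180 | 180 | 1.14 | 1.26 | 1.39 | 1.46 |
| SCRI | 365 | 365 | 1.05 | 1.09 | 1.12 | 1.15 |
| SCRI | 365 | 120 | 1.00 | 1.00 | 1.01 | 1.03 |
| SCRI | 365 | 60 | 1.00 | 1.00 | 1.01 | 1.02 |
| SCCS | 120 | 120 | 0.96 | 0.91 | 0.86 | 0.84 |
| SCCS | 180 | 180 | 0.99 | 0.97 | 0.94 | 0.92 |
| SCCS | 180 | 60 | 1.11 | 1.25 | 1.40 | 1.48 |

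Evaluating by whole days instead of continuously moves these figures by about 0.02 at most.

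**What removes the SCRI bias.**
- Requiring only that both windows end by the draw is not enough: D = V = 180 still gives 1.05 to 1.36.
- Ending follow-up one mean lag before the draw, with full windows required, still gives 1.02 to 1.15 at D = 180. At that cut-off only 1 − e^(−1) = 63% of events on the last day have been recorded.
- Ending it three mean lags before the draw (1 − e^(−3) = 95% recorded), with full windows, gives 1.00 to 1.02 wherever anyone is eligible.
- Eligibility then needs D of at least 84 + 3m, which is 126, 174, 264 and 354 days for the four lags. None of the four is met at D = 120, two are met at D = 180, and all four at D = 365. So 6 of the 12 combinations have no eligible vaccinees.

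**SCCS.** Ending follow-up 90 days before a draw at day 180 or 365 gives 0.99 to 1.01 for mean lags up to 30 days. At 60 to 90 days, where the cut-off is too short for the lag, it gives 0.95 to 1.11.

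**The case against.** The strongest reply is that this is a template. Section 9.2.2 says it is to be adapted, 9.1 makes a feasibility assessment necessary, and 9.3 already requires data lag to be reported. Section 9.2.3.3 asks for control periods free of event misclassification, and 9.7 asks for code counts over time, which could show a fall-off at the end of a series. The reference to data availability could be read as the date to which usable data exist, and a completeness date is often set in an analysis plan.

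Some of this stands: lag is not ignored, and a careful team could work out the cut-off. But 9.2.2 states an end date, and following it as written gives the bias. The adaptation notes do not prompt a lag cut-off. Counts over time reveal a deficit without correcting it. The event-date lagging in 9.6.5 addresses uncertain onset, not late records. Section 8 lets some wording be kept unchanged.

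The lag is also assumed, and the largest figures need a slow source, an early draw and vaccination up to the day of extraction. That is right and limits the claim.

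Two stronger readings should be resisted:
- A reader might infer that all self-controlled estimates are inflated. SCCS control time includes pre-vaccination time, which is the best recorded, and the bias turns downward when vaccination continues to the draw.
- A reader might infer that the affected designs are those the template prefers. Annex 3 recommends cohort analysis where data are already in electronic databases and marks all five designs suitable for acute onset. Section 9.8 says only that self-controlled designs suit acute events.

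**Conclusion.** The point holds in limited form. The end-of-follow-up rule admits incompletely recorded person-time, and the lag listed under 9.3 is never used to prevent this.

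For the SCRI and the same-person comparator in 9.1.1 the bias is upward. It is material when data are drawn soon after vaccination (about 1.14 to 1.46 at day 180 with vaccination continuing to the draw) and negligible when the draw is long after roll-out (1.00 to 1.03). For SCCS the direction depends on roll-out timing: 0.84 to 0.99 with vaccination up to draws at day 120 or 180, and 1.11 to 1.48 with a 60-day roll-out and a draw at day 180.

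The direction for the SCRI follows from the Protocol's placing of the control window, given any recording delay that is the same in both windows. The sizes rest on the assumed exponential delay, the assumed mean lags and uniform vaccination. A revision is worth making before the template is used for early draws.

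**What to change.** In 9.2.2 and Table 3, end follow-up in each data source at the earliest of the censoring conditions and the date up to which recording of the event under study is judged essentially complete. Set that date from the source's lag distribution, as part of the lag description in 9.3. Subtracting one mean lag from the draw date is not sufficient. For the SCRI and the same-person comparator, include only vaccinees whose full risk and control windows end by that date, and give the SCRI row of Table 3 the same explicit end.

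The change is a sentence or two and one completeness date per source and event; 9.3 asks for lag by source only, so event-specific lag would have to be added. The cost is timeliness. Recent vaccinees enter only at a later draw, and a very early draw from a slow-recording source may have no eligible SCRI subjects yet. In that case the protocol should say that the SCRI waits for a later draw.
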